6.5.4.3 Urinalysis

A clean-catch midstream urine sample (approx. 30 mL) will be obtained, in order to avoid contamination with epithelial cells and sediments, and allow proper assessments, as indicated in [Table 6-1](#).

Parameters to be evaluated by urine dipstick test will include specific gravity, pH, glucose, protein, bilirubin, ketones, nitrite, leukocytes and blood. Standard microscopic evaluation of urinary sediments will be performed if the urine dipstick test shows abnormalities.

Spot urine for calculation of protein to creatinine ratio can be aliquoted from the clean-catch urine specimen.

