Smoking history	X													

[figure not shown]
Periods	Screening		Treatment Period										Post Treatment Follow Up	Notes
	Week	-10 to -2	-2 ¹ (no later than) ²	BSL	2	4	8	12	16	24	32	40	48 ¹⁶ TD/EOT	
Vital signs	X	X	X	X	X	X	X	X	X	X	X	X	X	X
12-lead ECG ⁴	X								X				X	
Liver Biopsy ¹⁴		X											X	Biopsy to be performed no later than 2 weeks prior randomization
Adverse Events / Serious AE	X	X	X	X	X	X	X	X	X	X	X	X	X	X

[figure not shown]
Periods	Screening		Treatment Period										Post Treatment Follow Up	Notes
	-10 to -2	-2 ¹ (no later than) ²	BSL	2	4	8	12	16	24	32	40	48 ¹⁶ TD/EOT	52 EOS	
Modified AUDIT questionnaire ¹⁵		X	X	X	X	X	X	X	X	X	X	X	X	
Randomization via IRT			S											
Contact IRT	X	X	X	X	X	X	X	X	X	X	X	X	X	
Drug dispensing			S		S	S	S	S	S	S	S	S		
Drug administration record			X		X	X	X	X	X	X	X	X		
Drug compliance					S	S	S	S	S	S	S	S		
AHA Diet Review			S		S		S	S	S	S	S	S	S	
Diet Compliance			X				X		X			X	X	
Exercise assessment			S				S		S			S	S	
Blood collection														
Hepatitis serology ⁵	X													
Liver tests	X	X	X	X	X	X	X	X	X	X	X	X	X	
Serum BUN and Creatinine	X		X		X	X	X	X	X	X	X	X	X	
Coagulation panel	X	X	X				X		X			X		Only INR at screening visit 2

Periods	Screening		Treatment Period										Post Treatment Follow Up	Notes
	Week	-10 to -2	-2 ¹ (no later than) ²	BSL	2	4	8	12	16	24	32	40	48 ¹⁶ TD/EOT	
Hematology	X		X				X		X		X	X	X	
Clinical chemistry panel ⁷	X		X				X		X		X	X	X	
HbA1c	X													

Periods	Screening		Treatment Period										Post Treatment Follow Up	Notes	
	-10 to -2	-2 ¹ (no later than) ²	BSL	2	4	8	12	16	24	32	40	48 ¹⁶ TD/EOT			52 EOS
Urine															
Dipstick / routine Urinalysis with Reflex Micro	X		X		X	X	X	X	X	X	X	X	X	X	
Serum pregnancy test ¹²	X														
Urine pregnancy test ¹²		S	S	S	S	S	S	S	S	S	S	S	S	S	The urine pregnancy test should be performed every 4 weeks up to the follow up visit, including at week 20, 28, 36 and 44, and during any treatment extension period.
Drug screen	X		X												
Study Completion Form	X														

Periods	Screening		Treatment Period										Post Treatment Follow Up	Notes
	Week	-10 to -2	-2 ¹ (no later than) ²	BSL	2	4	8	12	16	24	32	40	48 ¹⁶ TD/EOT	

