
15 Appendix 3: Specific Renal Alert Criteria and Actions

Table 15-1 Specific Renal Alert Criteria and Actions

Serum Event	
Serum creatinine increase 25 – 49% compared to baseline	Confirm 25% increase after 24-48h Follow up within 2-5 days
Acute Kidney Injury: Serum creatinine increase \geq 50% compared to baseline	Follow up within 24-48h if possible Consider study treatment interruption Consider patient hospitalization /specialized treatment
Urine Event	
New dipstick proteinuria \geq 1+	Confirm value after 24-48h
Albumin- or Protein-creatinine ratio increase \geq 2-fold	Perform urine microscopy
Albumin-creatinine ratio (ACR) \geq 30 mg/g or \geq 3 mg/mmol;	Consider study treatment interruption / or discontinuation
Protein-creatinine ratio (PCR) \geq 150 mg/g or $>$ 15 mg/mmol	
New dipstick glycosuria \geq 1+ not due to diabetes	Blood glucose (fasting) Perform serum creatinine, ACR
New dipstick hematuria \geq 1+ not due to trauma	Urine sediment microscopy Perform serum creatinine, ACR
For all renal events:	
Document contributing factors in the eCRF: co-medication, other co-morbid conditions, and additional diagnostic procedures performed	
Monitor patient regularly (frequency at investigator's discretion) until either:	
Event resolution: sCr within 10% of baseline or protein-creatinine ratio within 50% of baseline, or	
Event stabilization: sCr level with \pm 10% variability over last 6 months or protein-creatinine ratio stabilization at a new level with \pm 50% variability over last 6 months.	

17 Appendix 5: The American Heart Association (AHA) Recommended Diet

Optimization of diet can result in a marked triglyceride-lowering effect that ranges between 20% and 50%. Good practices include weight loss, reducing simple carbohydrates at the expense of increasing dietary fiber, eliminating industrial-produced trans fatty acids, restricting fructose and saturated fatty acids, implementing a Mediterranean-style diet, and consuming marine-derived omega-3 PUFA.

AHA recommends the following:

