### **Adverse events of special interest / grouping of AEs**

Adverse events of special interest are the risks as described for both tropifexor and CVC (those that appear in tropifexor Development Safety Profiling Plan or CVC Investigator's Brochure, respectively). These will be summarized with absolute and relative frequency overall and by type of risk / AE.

Relative and absolute frequencies of patients with liver and renal events (see protocol Appendix 2 and 3, respectively) will also be provided.

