## **5.3 Laboratory parameters derivations**

### **5.3.1 Laboratory parameters**

Liver laboratory events will be classified in two ways:

- Events as defined in Appendix 2 of the protocol (Table 14-1). Only the laboratory results criteria will be considered. Confirmation of the results is not taken into account. For Table 14-1, criteria of ALT and AST are evaluated as either-or relationship, while those of baseline and treatment-emergent assessments as both-and relationship.
- Events as defined in the internal Novartis “Analysis plan for liver safety data”, Table 6-1.

[figure not shown]
Renal laboratory events will be classified in two ways:

- Events as defined in Appendix 3 of the protocol (Table 15-1). Only the laboratory results criteria will be considered. Confirmation of the results is not taken into account.
- Events as defined in the internal Novartis “Analysis plan for renal safety data”,

Criteria for other laboratory parameters:

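### The renal event table counts ACR and PCR criteria, but no readable passage requires these ratios at baseline or at any scheduled visit; the ratio part should be reported separately among patients tested

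*Protocol*

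**What the plan says.** SAP 2.8.1 (grouping of AEs) commits to a renal event summary: "Relative and absolute frequencies of patients with liver and renal events (see protocol Appendix 2 and 3, respectively) will also be provided". SAP 5.3.1 defines those events as "Events as defined in Appendix 3 of the protocol (Table 15-1). Only the laboratory results criteria will be considered", and adds "Confirmation of the results is not taken into account". A second classification, under an internal sponsor plan for renal safety data, is named but not reproduced.

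Protocol Appendix 3, Table 15-1, contains serum creatinine criteria (rise of 25–49%, or of 50% or more), new dipstick proteinuria, glycosuria and hematuria, and three ratio criteria. The first of these begins "Albumin- or Protein-creatinine ratio increase" and is set at 2-fold or more. The other two are absolute limits: ACR of at least 30 mg/g and PCR of at least 150 mg/g. The table's resolution rule also refers to a baseline PCR.

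On measurement, the urinalysis row of Table 6-1 reads "Dipstick / routine Urinalysis with Reflex Micro". Protocol 6.5.4.3 lists the dipstick parameters and closes with "Spot urine for calculation of protein to creatinine ratio can be aliquoted from the clean-catch urine specimen"; it does not mention urine albumin. The readable part of 6.5.4.2 lists no urine ratio. Section 7.4 defines its renal categories by creatinine and dipstick findings alone.

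**The concern.** A criterion can be compared across arms only if every patient has the same chance of meeting it. If ACR and PCR are measured only when another finding prompts them, a ratio event requires first being tested. A patient never tested cannot contribute one, and nothing in the SAP removes that patient from the denominator. The 2-fold criterion also needs a baseline ratio. The absolute limits in Table 15-1 do not say that the value must have been below the limit before treatment, so a raised ratio present at entry could count once a patient is tested, on a single unconfirmed value.

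Safety is the primary objective. Protocol 3.6 names renal function abnormalities as a potential tropifexor toxicity, and the rat combination studies in section 1.1 list the kidney among the primary target organs. The ratio rows could miss a real signal, or show an imbalance that reflects differences in testing.

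**Working it through.** **Step 1. Match each counted criterion to its scheduled measurement (readable text only).**

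| Table 15-1 criterion | Baseline scheduled? | Scheduled on treatment? | Must it be new since baseline? |
|---|---|---|---|
| Creatinine rise of 25–49%, or 50% or more | Yes (Table 6-1) | Yes, from Week 4 | Yes, defined relative to baseline |
| Dipstick protein, glucose, blood | Yes (Table 6-1, 6.5.4.3) | Yes, from Week 4 | Yes, each row says so |
| ACR or PCR rise of 2-fold or more | Not required | Not required | Needs a baseline ratio |
| ACR at least 30 mg/g; PCR at least 150 mg/g | Not required | Not required; ACR ordered after new glycosuria or hematuria | Not stated in the table |

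The mismatch is confined to the last two rows.

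**Step 2. Check the denominator.** SAP 2.8 performs safety analyses in the Safety Set. SAP 5.6 defines crude incidence as x/n, with n the patients at risk. Neither restricts n to patients with a ratio. That the denominator is the whole arm is therefore an inference from these two places, not a stated rule.

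**Step 3. Reproduce the plan's nearest safety figures.** Protocol 9.8.1 and SAP 3.1 use N = 50 and a beta prior (0.33, 0.33), so the posterior is Beta(0.33 + x, 50.33 − x).
- x = 0: P(incidence ≤ 5%) = 98.7% (plan 98.7%).
- x = 1: P(incidence ≤ 5%) = 86.7% (plan 86.6%).
- x = 10: P(incidence ≤ 20%) = 50.0% (plan about 50%).

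These reproduce. They presuppose that all 50 patients are assessed for the event. That holds for creatinine and dipstick, but the readable text does not secure it for the ratios.

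**Step 4. Illustrate the loss of detection.** The documents give no ratio event rate and no testing share, so both are assumed. With 5% true incidence and a share t tested independently of the event, P(at least one case in 50) = 1 − (1 − 0.05t)^50.
- t = 100%: 92%
- t = 50%: 72%
- t = 25%: 47%
- t = 10%: 22%

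If testing is more likely in patients who truly have the event, the loss is smaller.

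**Step 5. Illustrate the effect on the any-renal-event rate.** Let s be the share with a scheduled creatinine or dipstick event, r the true ratio-event rate among the rest, and t the share of the rest who are tested. The counted rate is s + (1 − s)·r·t. With s = 20% and r = 10% (assumed):
- t = 0: 20.0%
- t = 10%: 20.8%
- t = 25%: 22.0%
- t = 50%: 24.0%
- t = 100%: 28.0%

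Over s = 10–30% and r = 5–20%, moving from no testing to full testing shifts the rate by (1 − s)·r. That is from 0.7 × 0.05 = 3.5 points to 0.9 × 0.20 = 18 points. A between-arm gap in testing does much less: t = 10% against 50% gives 24.0 − 20.8 = 3.2 points, or 0.032 × 50 = 1.6 patients. The part s does not depend on t.

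**The case against.** The strongest reply has five parts.

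- **Unseen text.** Table 6-1 and 6.5.4.2 contain redactions, and the laboratory manual is not available. The ratios may be measured routinely. This stands: one can say only that no readable passage requires them. A reader might infer that no visit requires a ratio, or that the 2-fold criterion cannot be computed for anyone; the documents do not establish either.
- **The wording of 6.5.4.3.** The sentence may only say that no separate specimen is needed, not that the test is optional. That is a fair reading, but it still does not place a ratio at any visit, and it leaves ACR unmentioned.
- **Overlap with events already counted.** New glycosuria and hematuria, which prompt the ACR, are themselves Table 15-1 events, apart from the exceptions for diabetes and trauma. Patients tested for that reason mostly count already, so an any-event total moves little. This stands. It does not help the ratio rows, which would then describe mainly patients with another urine finding.
- **The condition of being new.** SAP 2.8.3 tabulates new notable laboratory results and points to 5.3.1, and protocol 9.5.2.2 restricts notable results to patients with normal baseline values. This partly answers the point about ratios raised at entry. However, the SAP does not clearly carry the condition over to the renal event count, and applying it needs a baseline ratio.
- **Blinding and randomization.** They limit arbitrary differences in testing between arms, though not differences arising from a drug effect on the triggers. Such an effect would itself appear in the scheduled dipstick rows.

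**Conclusion.** The point holds for the ratio-based part of the renal event table and for nothing wider. As written, the SAP counts ACR and PCR criteria for which the readable protocol secures neither a baseline nor a scheduled post-baseline value. Unless the redacted rows or the laboratory manual supply them, ratio events come from a selected subset, the 2-fold criterion may lack its reference value, and the absolute limits carry no explicit requirement in this count to be newly crossed.

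A reader might go further and conclude that the whole renal event rate by arm reflects who was tested, or that a false between-arm difference is to be expected. The documents do not support that: creatinine and dipstick criteria are scheduled in every arm, and triggered ACR tests fall mostly on patients already counted.

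The size of any distortion cannot be derived from the documents; the figures in the working rest on assumed rates and testing shares. The analysis is descriptive, with no hypothesis test at stake. This is a cheap improvement to an output that serves the primary safety objective.

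**What to change.** In SAP 5.3.1:
- Base the by-arm renal event count on the scheduled creatinine and dipstick criteria.
- Report the ratio criteria on separate rows. Use as denominator the patients with a baseline and at least one post-baseline ratio, and show that number by arm.
- Count the absolute ACR and PCR limits only when newly crossed since baseline.
- If ratios were not measured systematically, omit the ratio rows from the by-arm comparison.

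If ratios are in fact measured routinely, say so in protocol 6.5.4.3 and Table 6-1, naming the visits and covering ACR as well as PCR.

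The SAP change needs no new samples and can be made before database lock. Adding a baseline ratio was no longer an option at protocol Amendment 3, when enrollment had closed with 193 patients randomized. The cost is a smaller denominator, and so less precision, for the ratio rows.

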6.5.5 Electrocardiogram (ECG)

ECGs must be recorded after 10 minutes rest in the supine position to ensure a stable baseline. The preferred sequence of cardiovascular data collection during study visits is ECG collection first, followed by vital signs, and blood sampling. The Fridericia QT correction formula (QTcF) should be used for clinical decisions.

[REDACTED]

Single 12 lead ECGs are collected. The original ECGs on non-heat sensitive paper, appropriately signed, must be collected and archived at the study site. The original trace will be sent electronically for central review directly from the ECG machine.

A standard 12-lead ECG will be recorded at the visits indicated in [Table 6-1](#).

All ECGs must be performed on the ECG machines provided for the study.

All ECGs will be independently reviewed. Instructions for the collection and transmission of the ECGs to the independent reviewer will be provided in the ECG investigator manual.

12-lead ECG parameters (RR [Heart Rate], PR, QRS, and QT) are to be assessed.

Each ECG tracing must be labeled with study number, subject initials, subject number, date and time, and filed in the study site source documents.

In the event that a clinically significant ECG abnormality is identified at the site (e.g. severe arrhythmia, conduction abnormality of QTcF > 500 ms), the ECG is repeated to confirm the diagnosis and both ECGs sent to the core laboratory for expedited review if applicable.

Clinically significant abnormalities must be recorded on the relevant section of the appropriate CRFs capturing medical history/Current medical conditions/AE as appropriate.

6.5.6 Pregnancy and assessments of fertility

A positive test at Screening Visit and/or Baseline Visit is an exclusion criterion for participating in the study. The urine pregnancy test will be repeated every four weeks up to the follow up visit (see [Table 6-1](#)) including at weeks 20, 28, 36,44 and during any treatment extension period. The tests will be performed at the clinical center or at patient's home. In case of home pregnancy test, the patients will be provided with urine pregnancy test kits. The result must be provided to the investigator at next scheduled visit, in case of positive test the patient must contact investigator immediately. A positive urine pregnancy test after start of study drug requires immediate interruption of study drug until serum hCG is performed and found to be negative. If positive, the patient will enter the post-treatment follow up period. See also [Section 5.6.2](#).

Additional pregnancy testing might be performed if requested by local requirements.

6.5.7 Appropriateness of safety measurements

[figure not shown]
The safety assessments selected are standard for this indication/patient population and have been used in previous trials in this indication or deemed appropriate based on non-clinical and early clinical experience. Patients are seen frequently during treatment and will be assessed for safety parameters

[figure not shown]
6.6 Other assessments

No additional tests will be performed on patients/subjects entered into this study.

6.6.1 Clinical Outcome Assessments

6.6.1.1 Patient Reported Outcomes (PRO)

Trial feedback questionnaire

[figure not shown]
This trial will include an anonymized questionnaire, 'Trial Feedback Questionnaire' for subjects to provide feedback on their clinical trial experience. Individual subject level responses will not be reviewed by investigators. Responses would be used by the sponsor (Novartis) to understand where improvements can be made in the clinical trial process. This questionnaire does not collect data about the subject's disease, symptoms, treatment effect or adverse events

[figure not shown]

and therefore would not be trial data. Should any spontaneous information be collected about AEs, this would be transferred to the safety database.

6.6.2 Resource utilization

Not applicable.

7 Safety monitoring

7.1 Adverse events

An adverse event (AE) is any untoward medical occurrence (e.g. any unfavorable and unintended sign [possibly including abnormal laboratory findings - see below], symptom or disease) in a subject or clinical investigation subject after providing written informed consent for participation in the study until the end of study visit. Therefore, an AE may or may not be temporally or causally associated with the use of a medicinal (investigational) product.

In addition, all reports of intentional misuse and abuse of the product are also considered an adverse event irrespective if a clinical event has occurred.

The occurrence of adverse events must be sought by non-directive questioning of the patient at each visit during the study. Adverse events also may be detected when they are volunteered by the patient during or between visits or through physical examination findings, laboratory test findings, or other assessments.

Abnormal laboratory values or test results constitute adverse events only if they fulfill at least one of the following criteria:

- they induce clinical signs or symptoms,
- they are considered clinically significant,
- they require therapy.

Clinically significant abnormal laboratory values or test results must be identified through a review of values outside of normal ranges/clinically notable ranges, significant changes from baseline or the previous visit, or values which are considered to be non-typical in patient with underlying disease. Investigators have the responsibility for managing the safety of individual patient and identifying adverse events. Alert ranges for laboratory and other test abnormalities are included in [Appendix 1](#).

Adverse events must be recorded in the appropriate CRF capturing AEs under the signs, symptoms or diagnosis associated with them, accompanied by the following information:

- the severity grade:
 - mild: usually transient in nature and generally not interfering with normal activities
 - moderate: sufficiently discomforting to interfere with normal activities
 - severe: prevents normal activities
- its relationship to the study treatment
- its duration (start and end dates) or if the event is ongoing an outcome of not recovered/not resolved must be reported.
- whether it constitutes a serious adverse event (SAE - See [Section 7.2](#) for definition of SAE) and which seriousness criteria have been met
- action taken regarding [investigational] treatment
- its outcome (not recovered/not resolved; recovered/resolved; recovered/resolved with sequelae; fatal; or unknown)

All adverse events must be treated appropriately. Treatment may include one or more of the following:

- no action taken (e.g. further observation only)
- [investigational] treatment interrupted/withdrawn
- concomitant medication given
- non-drug therapy given
- patient hospitalized/patient's hospitalization prolonged (see [Section 7.2](#) for definition of SAE)

Once an adverse event is detected, it must be followed until its resolution or until it is judged to be permanent, and assessment must be made at each visit (or more frequently, if necessary) of

any changes in severity, the suspected relationship to the study drug, the interventions required to treat it, and the outcome.

Information about common side effects already known about the investigational drug can be found in the Investigator's Brochure (IB). This information will be included in the patient informed consent and should be discussed with the patient during the study as needed. Any new information regarding the safety profile of the medicinal product that is identified between IB updates will be communicated as appropriate, for example, via an Investigator Notification or an Aggregate Safety Finding. New information might require an update to the informed consent and has then to be discussed with the patient.

The investigator must also instruct each patient to report any new adverse event (beyond the protocol observation period) that the patient, or the patient's personal physician, believes might reasonably be related to study treatment. This information must be recorded in the investigator's source documents; however, if the AE meets the criteria of an SAE, it must be reported to Novartis.

7.2 Serious adverse events

7.2.1 Definition of SAE

An SAE is defined as any adverse event [appearance of (or worsening of any pre-existing)] undesirable sign(s), symptom(s) or medical condition(s) which meets any one of the following criteria:

- is fatal or life-threatening
- results in persistent or significant disability/incapacity
- constitutes a congenital anomaly/birth defect
- requires inpatient hospitalization or prolongation of existing hospitalization, unless hospitalization is for:
 - routine treatment or monitoring of the studied indication, not associated with any deterioration in condition
 - elective or pre-planned treatment for a pre-existing condition that is unrelated to the indication under study and has not worsened since signing the informed consent
 - treatment on an emergency outpatient basis for an event not fulfilling any of the definitions of a SAE given above and not resulting in hospital admission
 - social reasons and respite care in the absence of any deterioration in the patient's general condition
- is medically significant, e.g. defined as an event that jeopardizes the patient or may require medical or surgical intervention.

All malignant neoplasms will be assessed as serious under "medically significant" if other seriousness criteria are not met.

Life-threatening in the context of a SAE refers to a reaction in which the patient was at risk of death at the time of the reaction; it does not refer to a reaction that hypothetically might have caused death if it were more severe ([Annex IV, ICH-E12D Guideline](#)).

Medical and scientific judgment should be exercised in deciding whether other situations should be considered serious reactions, such as important medical events that might not be immediately life threatening or result in death or hospitalization but might jeopardize the patient or might require intervention to prevent one of the other outcomes listed above. Examples of such events are intensive treatment in an emergency room or at home for allergic bronchospasm, blood dyscrasias or convulsions that do not result in hospitalization or development of dependency or abuse ([Annex IV, ICH-E12D Guideline](#)).

Any suspected transmission via a medicinal product of an infectious agent is also considered a serious adverse reaction.

